5.3 VARIABLES COLLECTED

- Demographics: date of birth, sex, ethnicity, socioeconomic status (SES: education level, household income, marital status, employment status), household composition (multigenerational, single, married, cohabitating, children) and medical history

- **Weight, dietary and physical activity data.** Participants' reported/tracked weight, food intake and physical activity data via the WW mobile app or online website.
- Executive functioning as measured by the Behavior Rating Inventory of Executive Function® - Adult Version (BRIEF-A)
- Cognitive functioning: inhibitory control, attention, verbal working memory tasks, visuo-spatial working memory tasks, and working memory capacity tasks

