4.2 STUDY ARMS

WW (all participants; n = 30): All participants will receive pre-loaded computer tablets and 3-month access to the WW digital program. WW is a structured behavioral weight management program that focuses on diet, physical activity and mindset skills. The dietary approach is based on creating an energy deficit diet to produce weight loss while also being attentive to the quality of the calories. Specifically, the WW program assigns SmartPoints values to foods based on calories, sugar, saturated fat and protein. In addition, particular foods are assigned a points value of zero (0) to encourage a healthier eating pattern (e.g. fruits, vegetables, non-fat yogurt, fish). Upon sign-up, an individualized SmartPoints budget consisting of a daily SmartPoints target and weekly SmartPoints allowance is calculated based on height, weight, age and sex. The fitness component assigns FitPoints values to physical activities based on the type, duration, intensity and the participant's body weight. Participants receive 24/7 access to coaches, automatic enrollment in a rewards program based on behaviors, weekly emails motivating lifestyle changes and a closed social network for WW members.

WW + PolyRules! (50% of participants, n = 15): Participants assigned to the WW+ Polyrules arm will receive access to the WW online program (as described above) and to the PolyRules! app for three months. Participants will be trained on how to use PolyRules! via Zoom or Team Meeting platforms. Participants will be asked to engage in daily

cognitive training using the PolyRules! app for three months. They will be instructed to start with 20-min of daily cognitive training and to progressively increase their training time to 30-min. All interactions with PolyRules! will be passively recorded to monitor whether participants engage in cognitive training.

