4.3 MEASUREMENTS

Demographics

Participants will complete a questionnaire surveying: date of birth, sex, ethnicity, socioeconomic status (SES: education level, household income, marital status, employment status), household composition (multigenerational, single, married, cohabitating, children) and medical history.

Shared weight, dietary and physical activity data

As part of the WW experience, participants are instructed to track their weight, daily food intake and physical activity via the WW mobile app or online website. As a secondary objective, we will explore weight loss, dietary intake and physical activity over the course of the study and across study arms.

Cognitive Functioning

As a secondary objective, we will explore changes in attention, inhibitory control and working memory over the course of the study across study arms.

Executive Functioning

The Behavior Rating Inventory of Executive Function®- Adult Version (BRIEF-A) is a standardized measure of executive functions or self-regulation in everyday environment. The BRIEF-A assesses nine nonoverlapping theoretically and empirically derived clinical scales: Inhibit, Self-Monitor, Plan/Organize, Shift, Initiate, Task Monitor, Emotional Control, Working Memory, and Organization of Materials. BRIEF-A is available in English and Spanish and can be computer-administered.

Attention and Inhibitory Control Tasks

The *Cancellation Task* is a timed, tablet-based test of selective attention and inhibitory control, akin to D2 (Brickenkamp & Zilmer, 1998). There are two versions that can be used interchangeably: Cancellation Letters and Cancellation Pictures. Cancellation - Letters resembles the D2 in that it consists of similar stimuli: characters “d” and “p” with one to four dashes, arranged either individually or in pairs above or below the letters. For Letters, the participant must scan the items from left to right and select all “d”s with two dashes

(targets). In Cancellation - Pictures, letters are replaced with pictures of dogs and monkeys, some of which are rotated along the vertical axis or are presented upside down. For Pictures, the participant must select the upright dog (tail on the left) and the upside-down monkey (tail on right) separately in single blocks and together in a mixed block.

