5.4 SOURCE DOCUMENTS

- All data will be stored electronically in secure servers at Cedars-Sinai, with the exception of (1) WW shared weight, dietary and physical activity stored on the HIPPA-compliant WW platform and PolyRules! app usage data which will be stored on a HIPPA-compliant Amazon Web Services Server that is under the University of California business use agreement with Amazon.
- The surveys/questionnaires administered will be electronically based in REDCap, which is a survey platform on a Cedars-approved, secure network. The participant will be identifiable by a participant number which is linked to the participant in a separate, electronically secured location.
- The code list linking participant responses to their identity will be kept in a separate, electronically secured location. After analysis is complete, this list will be destroyed.
- Participants will be informed that audio recordings of semi-structured interviews will be kept until the completion of the study. Audio recordings will be transcribed and analyzed as soon as possible by the study team. After transcription has been completed, the audio recordings will be destroyed.
- Deidentified study data will be kept for 5 years after the study is completed. At the conclusion of the study, all study data will be destroyed.

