7.0 STATISTICAL CONSIDERATIONS

7.1 STUDY OUTCOME MEASURES

The primary objective of this study is to estimate the effect size in weight loss of supplementing the WW online program with gamified inhibitory control training (PolyRules!) among adults with overweight or obesity.

As a secondary objective, we will explore changes in dietary intake, physical activity, attention, inhibitory control and working memory over the course of study across study arms.

Primary endpoints

- Weight loss from baseline to 3 months.

Secondary endpoints

- As a secondary objective, we will explore dietary intake, physical activity, attention, inhibitory control and working memory over the course of the study and across study arms. We acknowledge that we are not powered to detect between-group difference on these outcomes. However, inasmuch as participants assigned to the WW only group do not engage in inhibitory control training, we expect no change in attention, inhibitory control and working memory over the course of the study among participants randomized to WW only.
- Qualitative outcomes measures will include participant's satisfaction with WW and PolyRules! (if applicable) and perceived benefits. Perceived satisfaction/dissatisfaction and preferred features of the WW and PolyRules! app will be qualitatively assessed and data obtained in semi-structured interviews will be summarized.

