7.3 STATISTICAL ANALYSES

Descriptive analysis will be presented with mean \pm standard deviation for quantitative variables, and frequency (percentages) for qualitative variables. A 95% confidence interval for the difference in weight loss between WW and WW + PolyRules! will be calculated. Cognitive test scores (inhibitory control, attention, verbal working memory tasks, visuo-spatial working memory tasks, and working memory capacity tasks), executive function, and physical activity questionnaires will be scored and summarized (Mean and SD) by group and used to inform the design of a larger randomized controlled trial. Calculations will be performed using R-package, version 4.0.⁵³

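### The 3-month weight behind the primary endpoint has no stated source except WW self-tracking, and the three-valid-days rule excludes randomised participants by engagement, unequally between arms

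*Combined protocol and SAP*

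**What the plan says.** Section 7.1 names one primary endpoint: "Weight loss from baseline to 3 months". Section 7.3 gives its analysis: "A 95% confidence interval for the difference in weight loss between WW and WW + PolyRules! will be calculated". Estimating this effect is the pilot's stated purpose (2.1, 7.1).

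Three places say where weight comes from, and they agree:
- 4.3: "participants are instructed to track their weight, daily food intake and physical activity via the WW mobile app or online website".
- 5.3, the variables list: "reported/tracked weight, food intake and physical activity data via the WW mobile app or online website".
- 5.4, storage: "WW shared weight, dietary and physical activity stored on the HIPPA-compliant WW platform".

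Section 4.1 describes the baseline and post-intervention assessments as demographic and medical history questionnaires plus a cognitive battery. Section 5.2 times only questionnaire data at those two points. The Schedule of Procedures names both assessments without itemising them.

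Two other weights are implied near enrolment. One lies behind the BMI criterion in 3.2. The other is used at WW sign-up, where the "daily SmartPoints target and weekly SmartPoints allowance is calculated based on height, weight, age and sex" (4.2). Neither is named as the study baseline.

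Section 5.2 also sets an inclusion rule. A participant's data enter the analysis only with at least three valid days of WW interaction and, where applicable, PolyRules! use.

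Section 4.3 places weight loss under a secondary objective: "As a secondary objective, we will explore weight loss, dietary intake and physical activity over the course of the study and across study arms". Section 7.1 makes it primary and does not list it among the secondary endpoints.

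**The concern.** Weight logging in an app is itself a form of engagement with the programme. If it is the only source of the 3-month weight, the endpoint is observed only in those who keep logging. The study would still be in contact with some of the others, because they complete the post-intervention assessment, yet the plan gives no way to use that contact to obtain the endpoint. The loss costs precision in a trial of 30. It also causes bias if the people lost differ in weight loss from those kept and this does not cancel between arms.

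The 5.2 rule acts in the same direction. It selects on behaviour after randomisation, and the selection differs by arm: a WW + PolyRules! participant who uses WW but hardly opens PolyRules! is dropped, while a WW-only participant with the same WW use is kept. The remaining comparison is no longer between the groups as randomised.

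**Working it through.** The plan derives no figure on this point. Section 7.2 sets 30 participants by funding, with no SD, drop-out rate or effect size. The check is therefore a reading of the text, followed by arithmetic for scale only.

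**Text**
1. Baseline value: everyone who starts WW supplies a weight at sign-up (4.2). It is not labelled as baseline, but it exists in the named data source.
2. 3-month value: no section gives a source other than logged entries, a window around 3 months, or a rule for choosing among entries.
3. Inclusion rule: 5.2 counts days of app interaction, not weights. It can admit someone with no weight near 3 months and exclude someone who has one.

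**Precision**

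Inputs: 15 per arm (4.1 and 4.2), equal arms, common SD of weight change, 12 assessment completers per arm (assumed).

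95% CI half-width in SD units = t(0.975, 2n - 2) x sqrt(2/n)

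| n per arm with an endpoint value | Half-width (SD) | Against n = 12 |
|---|---|---|
| 15 | 0.748 | |
| 12 | 0.847 | reference |
| 11 | 0.889 | 5% wider |
| 10 | 0.940 | 11% wider |
| 9 | 0.999 | 18% wider |

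Only the rows below 12 represent completers lost through non-logging, which an assessment weight could recover. The step from 15 to 12 is study drop-out, which it would not recover. If no completer lacks a logged weight, the gain in precision is zero.

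**Bias**

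In one arm, let m be the share without a usable weight and g the mean weight loss of loggers minus that of non-loggers. The loggers' mean exceeds the whole arm's mean by m x g. For the between-arm difference:

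bias = m1 x g1 - m2 x g2

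- Unequal logging with a common gap, all values assumed: shares 3/12 and 1/12 differ by 0.167. With g = 0.25 SD the bias is 0.167 x 0.25 = 0.04 SD. With g = 1.0 SD it is 0.17 SD.
- Equal logging with different gaps, all values assumed: shares of 2/12 in both arms, gaps of 1.0 and 0.5 SD, give 0.167 x (1.0 - 0.5) = 0.08 SD. Equal logging alone does not remove the bias.

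The same formula covers the 5.2 rule, with m the share excluded and g the gap between those included and those excluded. Because of the PolyRules! condition, m can differ between arms even when WW use is identical.

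**The case against.** The strongest reply is that this argues from silence. The assessment lists are plainly incomplete: 7.3 says physical activity questionnaires will be scored, yet no such questionnaire is described in 4.1, 4.3, 5.2 or 5.3, and 4.1 omits the exit interview that the schedule includes. Section 6.2 promises standardised measurement in general terms. A weight may therefore be taken at the assessments without being written down. That stands, and it makes the missing-route point conditional. It does not touch the 5.2 rule, which is explicit.

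Three stronger readings are tempting, and the documents do not support them:
- That there is no baseline weight. The sign-up weight in 4.2 exists for those who start WW; what is missing is its designation.
- That WW access lapses before the endpoint can be logged. Section 4.2 states "All participants will receive pre-loaded computer tablets and 3-month access to the WW digital program", and an entry late in those 3 months can serve as a 3-month weight. No earlier lapse is stated.
- That equal logging in the two arms would guarantee an unbiased estimate. As shown, this also needs the gap between loggers and non-loggers to be the same in both arms, or no gap at all.

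It can also be said that this is a funding-limited pilot reporting one interval, with no test or progression threshold, and that the illustrated bias is small beside the half-width. Both are fair. They limit the severity. They do not remove the case for an inexpensive change to the pilot's one primary estimate.

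**Conclusion.** The concern holds in limited form. Self-tracking in WW is the only stated source of weight, and the 3-month value is the weak part: unless the assessments include an unstated weight, participants who stop logging but complete the post-intervention assessment have no stated route to an endpoint value. Independently of that, the 5.2 rule as written removes randomised participants by post-randomisation engagement, with an extra condition in one arm.

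The size is unknown, because the documents give no rate of non-logging or exclusion. Under the assumed 12 completers per arm, losing 1 to 3 per arm widens the interval by 5% to 18%. The illustrated biases run from 0.04 to 0.17 SD, against a half-width of 0.85 SD or more. All the shares and gaps are assumed. The change should be made because the weight is the sole primary endpoint and collecting it is inexpensive. The documents do not show that the estimate will be seriously wrong.

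**What to change.** 1. In 5.2, state that the three-valid-days rule does not apply to the primary weight analysis, which includes all randomised participants with weight data in the arm assigned. Any engagement-based set is supportive. Without this step, the added weights would still be discarded for the least engaged.
2. In 4.3, 5.3 and the schedule, add a dated self-weighed body weight at the existing baseline assessment, before randomisation, and at the existing post-intervention assessment. Seek it from all randomised participants, including those who stopped using WW. If such weights are already taken, say so.
3. In 7.1, define the endpoint as the difference between the two readings within a window around 3 months that the team sets. If the baseline reading is missing, use the WW sign-up weight. If the 3-month reading is missing, use the logged weight nearest 3 months within the window. Report by arm the source of each value and the number missing.
4. Reconcile 4.3 with 7.1. If the secondary weight loss in 4.3 means the tracked trajectory during the study, say that.

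The cost is one extra item at each of two assessments, wording in 4.3, 5.2, 5.3 and 7.1 and a line in the schedule, and some follow-up contact with participants who have disengaged. Section 4.2 lists tablets and WW access but no scale, so the weights depend on participants' own scales and remain unblinded self-reports. Timing and completeness improve; blinding does not. Naming a window and a selection rule within the WW data alone would need no new collection, but it would not recover completers who stopped logging.

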5.4 SOURCE DOCUMENTS

- All data will be stored electronically in secure servers at Cedars-Sinai, with the exception of (1) WW shared weight, dietary and physical activity stored on the HIPPA-compliant WW platform and PolyRules! app usage data which will be stored on a HIPPA-compliant Amazon Web Services Server that is under the University of California business use agreement with Amazon.
- The surveys/questionnaires administered will be electronically based in REDCap, which is a survey platform on a Cedars-approved, secure network. The participant will be identifiable by a participant number which is linked to the participant in a separate, electronically secured location.
- The code list linking participant responses to their identity will be kept in a separate, electronically secured location. After analysis is complete, this list will be destroyed.
- Participants will be informed that audio recordings of semi-structured interviews will be kept until the completion of the study. Audio recordings will be transcribed and analyzed as soon as possible by the study team. After transcription has been completed, the audio recordings will be destroyed.
- Deidentified study data will be kept for 5 years after the study is completed. At the conclusion of the study, all study data will be destroyed.

5.5 DATA COLLECTION AND STORAGE

- Participants' consent forms will be stored in a password protected folder in Box, which is located in secure servers at Cedars-Sinai.
- A unique participant number will be used for all the data so that it can be traced back to the consent form should the participant wish to withdraw.
- Information on participants' demographics data will be stored in REDCap separate from the participant's identifying information.
- Audio data (from semi-structured interviews) will be securely stored in a Box folder. Access to audio data will be strictly monitored and limited to study staff. All audio data will be transcribed and analyzed at the earliest opportunity. After transcription, the audio files will be destroyed.

5.6 CONFIDENTIALITY AND SECURITY OF DATA

- All data will be stored electronically in secure servers.
- A unique participant number will be used for all the data so that it can be traced back to the consent form should the participant wish to withdraw. The unique participant number will be kept in a REDCap database which will be separate from the data and consent documents.
- Information on participants' demographics data will be stored in REDCap separate from the participant's identifying information.
- Only IRB approved study staff and the PI will have access to the data collected. Personal and sensitive data will be stored for 5 years and will be destroyed after this time by the PI.

6.0 DATA AND SAFETY MONITORING

6.1 DATA AND SAFETY MONITORING PLAN

- All data will be stored electronically in secure servers (REDCap, Amazon Web Services)
- The Box folder containing the consent forms will be password protected.
- The audio recordings stored in a Box folder will also be password protected.
- The PI will be responsible for data and safety monitoring for this study.
- Any deviations from the research protocol or unexpected problems will be reported promptly to the Cedars-Sinai IRB.

6.2 QUALITY CONTROL AND QUALITY ASSURANCE

Principles underlying our approach to quality control include:

- Standardization of measurements
- Use of clear and specific protocols for all study activities including training for data collection and processing
- Validation and verification of data management procedures by using software capable of checking for out-of-range values and other sources of outliers
- Implementation of a data cleaning protocol
- Confidentiality will be strictly maintained during all data management
- The research team will follow aforementioned schemes to collect and manage study data by maintaining consistent quality and security of the study observations.

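### The primary outcome rests on weights participants enter themselves, with no weighing conditions and no check against a scale reading, which leaves avoidable noise and room for differential reporting

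*Combined protocol and SAP*

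**What the plan says.** The primary endpoint in section 7.1 is "Weight loss from baseline to 3 months", and section 7.3 plans a 95% confidence interval for the difference in it between arms.

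On the source of the weights, section 4.3 says that "participants are instructed to track their weight, daily food intake and physical activity via the WW mobile app or online website". Section 5.3 lists the variable as "Participants' reported/tracked weight, food intake and physical activity data via the WW mobile app or online website". On equipment, section 4.2 says that "All participants will receive pre-loaded computer tablets and 3-month access to the WW digital program"; a scale is not mentioned. Sections 4.1 and 5.2 describe the assessments at enrollment and after the intervention as questionnaires and a cognitive battery, and the Schedule of Procedures in 4.3 has no row for weighing. Section 4.2 says the SmartPoints budget is "calculated based on height, weight, age and sex", without saying how that weight is obtained.

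Section 6.2 gives "Standardization of measurements" as a principle. It adds specific procedures with training, software checks for values outside the expected range and for outliers, and data cleaning. None of these is tied to weight.

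Only the WW + PolyRules! arm has the added task ("Participants will be asked to engage in daily" cognitive training, section 4.2). The documents mention neither a sham app nor blinding.

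**The concern.** The point is how each weight is taken. It would remain even if the plan named exactly which entries count as the baseline and 3-month weights.

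Section 4.3 specifies the secondary cognitive tasks down to trial counts and stimulus durations, but for the primary outcome it gives only a tracking instruction. Someone following the plan as written could use a different scale, time of day or clothing at the two weighings. Errors that differ between the two weighings do not cancel in a change score, and they widen the interval for the primary comparison.

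The more serious risk is differential reporting. If people who know their arm shade their entries differently on average, the estimated difference is biased, and a larger sample would not remove that. A plausible but shaded value passes a range check. The pilot exists to estimate this one effect size and to inform a larger trial, so both problems fall on its main product.

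**Working it through.** **Inputs from the documents.** N = 30 (4.1), with 15 allocated to WW + PolyRules! (4.2), leaving 15 on WW only; 95% confidence interval (7.3). Section 7.2 bases N on funding and gives no SD, effect size, power or dropout rate, so there is no precision figure to reproduce.

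**Assumptions.** True SD of 3-month change s = 4 kg (range 3 to 5). Error SD per weighing e = 0.5 to 1 kg, independent at the two weighings.

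**Random error.** Observed SD of change = √(s² + 2e²). Half-width = t(0.975, 28) × SD × √(2/15), with t = 2.048 and √(2/15) = 0.365.

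- s = 4, e = 0: SD 4.00; half-width 2.99 kg.
- s = 4, e = 0.5: SD = √16.5 = 4.06; half-width 3.04 kg (+0.05).
- s = 4, e = 1: SD = √18 = 4.24; half-width 3.17 kg (+0.18).

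The equivalent sample size is 30 × (s/SD)²: 30 × 16/16.5 = 29.1 at e = 0.5, and 30 × 16/18 = 26.7 at e = 1.

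Half-widths in kg over the range of s, 15 per arm:

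| s | e = 0 | e = 0.5 | e = 1 |
|---|---|---|---|
| 3 | 2.24 | 2.31 | 2.48 |
| 4 | 2.99 | 3.04 | 3.17 |
| 5 | 3.74 | 3.78 | 3.89 |

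With 12 per arm (an assumed 20% dropout) and s = 4, the half-width goes from 3.39 kg to 3.44 kg (e = 0.5) or 3.59 kg (e = 1).

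These figures count all weighing error. Ordinary day-to-day variation remains under any instruction, so they bound the gain from above.

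**Differential reporting.** If one arm's reported change is shaded by b kg on average, the difference moves by b. With s = 4 and 15 per arm, the standard error is 4 × 0.365 = 1.46 kg. The noncentral t distribution then gives true coverage of the nominal 95% interval of 93.7% at b = 0.5 kg and 89.9% at b = 1 kg. Both values of b are illustrations; the documents give no size for b.

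**The case against.** Several stronger readings are tempting, and the documents do not support them.

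- *No check of the value exists.* Section 6.2 names range and outlier checks and data cleaning. What is absent is verification against a scale reading.
- *Section 6.2 is contradicted.* It states principles and promises specific procedures with training. Weighing instructions could sit in working documents outside this plan. The gap is that the plan does not apply its principle to its main variable.
- *Every weight comes from someone who knows the arm.* BMI is an inclusion criterion (3.2), and screening is by phone or REDCap (3.4), so a weight was probably given before allocation. It is not named as the endpoint baseline. The Schedule of Procedures puts application set-up under the intervention, after randomization, so WW entries probably follow allocation. Both are inferences.
- *The noise costs a large share of the sample.* That needs errors of about 2 kg per weighing, which the documents do not support. A constant scale offset or habitual clothing cancels in a change score.
- *Shading will occur.* Both arms use the same WW programme and rewards, and the gift card is for completing procedures. Shading common to both arms cancels.
- *The SD is necessarily inflated for the larger trial.* If that trial also used WW-tracked weights, the observed SD would be the right planning input.

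What stands is that no passage sets weighing conditions or verifies a value, and the arms differ visibly. The noise is second to the imprecision of 15 per arm, and the point presupposes that the two endpoint weights are identified.

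**Conclusion.** The concern holds in a limited form. As written, the plan produces primary-outcome weights that are unstandardised, unverified against a scale, and entered by participants who can be expected to know their arm. That last part is inferred from the design.

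At an assumed true SD of 4 kg and an error of 0.5 to 1 kg per weighing, the noise adds at most 0.05 to 0.18 kg to a 95% half-width of 2.99 kg. Across SDs of 3 to 5 kg the addition is 0.04 to 0.24 kg. This alone would not change the trial's conclusions.

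The stronger reason to act is that differential reporting would shift the primary estimate one for one, and nothing in the plan would reveal it. A reader might infer that the estimate will be biased. The documents show only that it could be, and the size is unknown. The change is worth making because it is cheap and delivers what section 6.2 already promises.

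**What to change.** In section 4.3, give both arms the same written instruction for the two weights that form the primary endpoint: same scale both times, in the morning before eating, light clothing, no shoes, and entered in WW the same day.

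Have the baseline weighing done at the baseline assessment, before the participant is told the arm. If WW is not yet set up that day, record the value with the baseline questionnaire in REDCap and copy it into WW at set-up.

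Ask for a photo of the scale display at both weighings, stored under the participant number with the other study data. Where no photo exists, keep the typed value, so that nobody is excluded. Report by arm how many weights were confirmed, since unequal confirmation would itself need comment. A photo confirms the displayed number only; the conditions still depend on the instruction.

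The cost is one instruction sheet, two photos per participant, a slight participant burden and a little photo handling by existing staff. Some photos will be missing. No visits or purchased scales are needed.
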